Antiplatelet therapy guided by thrombelastography in patients with
acute coronary syndromes (TEGCOR Study)

Principal Investigator:

[name].
Krannert Institute of Cardiology
[name]
[name]

A. INTRODUCTION

Platelet aggregation and activation mediated by various agonists are fundamental in the development of ischemia in patients with coronary artery disease.

Activated platelets mediate vessel wall inflammation, and thrombin generated by procoagulant factors and tissue injury initiates fibrin generation. Platelet-platelet aggregates cross-linked by fibrin and fibrinogen eventually mechanically obstruct the vessel lumen in patients with acute coronary syndromes. Dual antiplatelet therapy with aspirin and clopidogrel and more recently aspirin and prasugrel have become standard of care for patients undergoing percutaneous coronary intervention (PCI) and stent placement for acute coronary syndromes. Despite significant reduction in ischemic complications, concern remains regarding the occurrence of thrombotic events after coronary interventions and stenting. Specifically, high posttreatment platelet reactivity after coronary stenting measured by ex vivo platelet assays with clopidogrel have been repeatedly associated with high rates of stent thrombosis and myocardial infarction post PCI, events with high mortality and morbidity [1-3]. The significant interindividual variation in the extent of clopidogrel platelet inhibition is to a great degree founded in genetic interindividual differences in CYP450 metabolism or other drug-drug interactions that inhibit hepatic isoenzyme activity [4,5]. In particular reduced function polymorphisms of CYP 2C19 have been found to significantly impair the pharmacodynamic effects of clopidogrel and have been associated with worse clinical outcomes in several large studies of patients after coronary stent implantation [6]. These findings have supported the development of more efficacious and predictive P₂Y₁₂ inhibitors, such as prasugrel and ticlopidine, both of which have been shown to be associated with reduced rates of stent thrombosis as compared to clopidogrel.

Thrombelastography (TEG) is an ex-vivo method that measures the viscoelastic properties of whole blood clot formation in response to various agonists [2]. In essence, the device features a stationary pin suspended by a torsion wire which is lowered into a rotating sample cup containing whole blood and various agonists. The device then measures the forces between the pin and the cup generated by the developing fibrin and platelet-fibrin clots.

Thus, the method enables the measurement of various parameters of coagulation and aggregation, including thrombin activity by measuring the time to fibrin generation, but also the relative contribution of platelet-platelet aggregate formation and fibrin generation on tensile clot strength. As we have shown previously, elevated whole blood clot strength appears to be a significant predictor for adverse ischemic events after coronary stenting with a relative adjusted OR of 22.6 for the occurrence of ischemic events in patients with highest quartile clot strength [2]. Inhibition of GpIIb/IIIa receptors by eptifibatide significantly reduces MA and also periprocedural myocardial infarctions associated with coronary stenting. It appears that high tensile whole blood clot strength on clopidogrel therapy appears to be a significant risk factor for recurrent ischemic events that may be only partially explainable by insufficient P₂Y₁₂ receptor inhibition. The ex-vivo phenotype of high tensile clot strength is probably multifactorial, but may be due to release of tissue factor and increased velocity of thrombin generation in patients with acute coronary syndromes. Not surprisingly, it is these patients that are clinically known to be at highest risk for recurrent thrombotic events and cardiac death. Accordingly, we have previously demonstrated that high clot strength phenotype was associated with

elevated levels of fibrinogen, tissue factor, vWF, C-reactive protein, TNF- α and IL-8 and was found more frequent in patients with acute coronary syndromes as compared to patients with stable coronary artery disease [7,8]. These findings suggest that TEG may be a unique testing modality that is able to identify and specifically target patients at elevated clinical risk.

Although increased P₂Y₁₂ receptor inhibition with prasugrel is more efficient in reducing ischemic events than clopidogrel, it also carries an increased risk for significant bleeding. Personalized treatment approaches should ideally be able to identify patients at need for higher or lower intensity of platelet P₂Y₁₂ inhibition in an attempt to optimize the risk/benefit ratio for each patient. However, currently only one study prospectively compared a personalized dosing approach of clopidogrel vs. standard dosing in 162 patients prior to coronary stenting [9].

In addition to the currently available antiplatelet drugs that inhibit ADP mediated platelet aggregation by inhibiting P₂Y₁₂, several oral thrombin receptor protease-activated receptor-1 (PAR-1) inhibitors (platelet thrombin receptor) have been developed. Two oral PAR-1 inhibitors have completed phase 2 clinical trials and the eventual addition of these drugs to standard dual antiplatelet therapy may in the future further increase bleeding risk for patients on several antiplatelet drugs. Theoretically, thrombelastography may provide an ideal methodology to identify patients at highest risk for thrombin mediated ischemic events or identify patients at risk of bleeding. In the surgical field, thrombelastography has been used successfully to predict postoperative bleeding risk and guide post surgical and trauma related transfusion requirements.

Currently controversy exists as to the optimal method to identify patients at risk for ischemic events after coronary interventions and several point of care assays measuring platelet inhibition are currently in use in large prospective clinical trials. These currently employed methods focus on the specific amount of ADP mediated platelet aggregation measured ex-vivo to guide risk prediction and intensity of P₂Y₁₂ inhibition by either dose adjustment of clopidogrel or switching therapy to prasugrel. Therefore, as a control group we will include a group of patients which will be assigned to prasugrel or clopidogrel therapy based on LTA measurements pre-cath using a cutoff that has been validated as a predictor of ischemic events in several other large studies [1].

The purpose of this study is to assess the pharmacodynamic effects of high intensity P₂Y₁₂ receptor inhibition by prasugrel in patients with high clot strength and assess the interrelationship with clopidogrel non-response as defined by light transmittance aggregometry. Pharmacogenetic analyses will aid in understanding the impact of CYP450 metabolism and other polymorphisms in the coagulation cascade on the high clot strength phenotype.

Data from this study may be used in the design of personalized therapeutic trials of antiplatelet drugs and guide the use of next generation PAR-1 inhibitors.

B. SPECIFIC AIMS

The aim of the current study is to evaluate the impact of increased P₂Y₁₂ inhibition by prasugrel on the physical properties of whole blood clot formation in patients with

persistent high fibrin-platelet clot strength on clopidogrel and compare the TEG guided treatment approach to a platelet aggregation guided approach of personalized antiplatelet therapy.

Pharmacogenetic analyses of relevant genetic polymorphisms and genes involved in thrombosis are intended to support pharmacodynamic conclusions drawn from the results of this study.

Primary hypothesis

High tensile clot strength as measured by TEG and defined as MA \geq 69 on clopidogrel is partially due to inadequate P₂Y₁₂ inhibition and can be overcome by switching to prasugrel

Primary Endpoint:

Persistence of high tensile clot strength measured by TEG 16-24 hours after reloading of either clopidogrel or prasugrel.

Secondary Endpoints:

- a) Occurrence of ischemic events over 6 month follow-up period as defined by death, recurrent myocardial infarction, recurrent unstable angina, repeat coronary intervention (exclusion of staged interventions)
- b) Occurrence of bleeding events according to TIMI minor/major criteria over 6 months follow-up.

C. METHODS

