2.0 Enrollment/Randomization

The current study will be an open label study. Subjects will be enrolled among patients who are admitted with an acute coronary syndrome (unstable angina, non-STEMI) and who are being referred for coronary angiography and possible percutaneous coronary intervention. All study candidates must have received at least 300mg of clopidogrel loading dose since admission, or have been on clopidogrel 75mg daily for >5 days at time of enrollment.

Subjects will be enrolled before undergoing diagnostic angiography using written informed consent after screening for appropriate candidates. Patients will have the first study blood draw performed prior to coronary angiography. In case significant coronary disease is found and the patient proceeds with percutaneous coronary intervention, the patient will be randomized to either a TEG guided or LTA guided strategy. The subject will then be switched to prasugrel or continue on clopidogrel according to the results of the pre-cath TEG or LTA measurements. Patients in the TEG guided arm with high physical clot strength ($MA \geq 69$) will be assigned to prasugrel, whereas patients with lower clot strength ($MA < 69$) will continue on clopidogrel. This cutoff reflects the 50th percentile of clot strength based on data from a prior cohort of patients undergoing PCI and was determined as cutoff for ischemic risk in prior studies.

Patients in the LTA guided arm with high on treatment platelet reactivity to ADP ($PA > 42.9\%$) will be assigned to prasugrel, whereas patients with low on treatment platelet reactivity ($PA \leq 42.9\%$) will continue on clopidogrel. This value was determined as a significant cutoff for ischemic risk in prior studies. If the decision is made to proceed with percutaneous revascularization, patients assigned to remain on clopidogrel will receive 300mg clopidogrel loading dose in the cath lab, and then remain on 75mg po daily. Patients assigned to prasugrel will receive 60mg po loading dose, and then remain on 10mg po daily.

Telephone follow-up will be conducted after 6 months to assess for ischemic and bleeding events.

The enrollment and study process is depicted in a Fig 1.

We plan on enrolling 100 subjects, with 50 subjects randomized to each arm:

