4.5 Study Withdrawal/Discontinuation

Participants may withdraw from the participation in the study at any time. This requires a written request to the principal investigator.

5 Statistical Considerations

Sample size calculation was performed assuming an estimated prevalence of 50% of MA ≥ 69 in the general patient population with ACS on clopidogrel referred for cardiac catheterization according to previous studies. It was assumed that switching to prasugrel would reduce the maximal clot strength in 60% of these patients with baseline MA ≥ 69 resulting in 20% prevalence of high tensile clot strength. Assuming a power of 0.8 and alpha 0.05 with a loss of 5% of follow-up, a sample size of 50 in each arm and a total sample size of n=100 was calculated accordingly.

6 Privacy/Confidentiality Issues

All information will be collected and kept on a customized database on computers of the investigators and on a secure network server at the Krannert Institute of Cardiology. Access to the database is password protected and computers will be kept in locked offices at the Krannert Institute and Wishard Hospital. Access to the offices housing the information is only available via keys possessed by the investigators. Only the listed investigators of the study will have access to review information and to analyze data. Data sent for analysis will be de-identified. The names of the patients will not be revealed if the results of this study lead to a publication.

The genetic information found through the course of the study will not be revealed to the study participants or their family members.

Blood samples are stored in a secured biospecimen storage facility that has secured access. Biospecimens are deidentified and do not allow identification of patients.

7 Follow-up and Record Retention

The study will last for at least 6 months after enrollment of the last study subject. Records and samples will be kept as required by the IRB and federal legislation and until completion of all study related analyses.

D. FACILITIES AVAILABLE

The cardiac catheterization laboratories at Wishard Hospital and Methodist Hospital will be used as study locations as required for the clinical care of the patients. Standard hospital care will be provided.

Laboratory analyses including platelet studies, thrombelastography, as well as DNA analysis will be performed in the laboratories of the Division of Clinical Pharmacology, Indiana University School of Medicine.

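### The primary hypothesis concerns switching patients with MA ≥ 69 to prasugrel, but only the guidance strategy is randomised, and Section 5 sizes two arms from one population's before and after rates

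*Protocol*

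**What the plan says.** - **Endpoint (Section B):** "Persistence of high tensile clot strength measured by TEG 16-24 hours after reloading of either clopidogrel or prasugrel". It gives a measurement and a time, and no groups to compare.
- **Primary hypothesis (Section B):** high MA on clopidogrel "is partially due to inadequate P₂Y₁₂ inhibition and can be overcome by switching to prasugrel". This is a statement about change after a switch in patients who start at MA ≥ 69.
- **Aim (Section B):** it has two halves. One is to "evaluate the impact of increased P₂Y₁₂ inhibition by prasugrel on the physical properties of whole blood clot formation in patients with" persistently high clot strength on clopidogrel; the other is to "compare the TEG guided treatment approach to a platelet aggregation guided approach of personalized antiplatelet therapy".
- **Randomisation (Section 2.0):** "the patient will be randomized to either a TEG guided or LTA guided strategy". Drug is not randomised. In the TEG arm it follows baseline MA (prasugrel at 69 or above, clopidogrel below). In the LTA arm it follows PA with a cutoff of 42.9%, so that arm also contains prasugrel patients.
- **Sample size (Section 5):** 50% of patients have MA ≥ 69 on clopidogrel. Switching clears 60% of these, leaving 20%. With power 0.8, alpha 0.05 and 5% loss, this gives "a sample size of 50 in each arm".

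**The concern.** The hypothesis, the randomisation and the sizing describe different comparisons. The hypothesis asks whether high MA falls once prasugrel is given. The randomisation can answer whether one guidance strategy leaves fewer patients with high MA than the other. The sizing takes its two rates from the first question and its two arms from the second.

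This matters because the comparison nearest to the hypothesis is the one without a control. Patients are switched in the TEG arm because their MA was high at one measurement. Some will be below 69 at the next measurement whatever drug they take. A fall could then be reported as confirming the primary hypothesis with no prasugrel effect behind it.

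Comparing all patients by drug received is no better. In the TEG arm the drug is determined by the baseline value of the endpoint variable, so such a comparison largely reads back the baseline split.

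**Working it through.** **1. The plan's own figure.** For 50% versus 20%, two-sided 0.05, power 0.8:

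n = [1.96·√(2·0.35·0.65) + 0.842·√(0.25 + 0.16)]² / 0.30² = 38.5 per arm.

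With continuity correction: (38.5/4)·[1 + √(1 + 4/(38.5·0.30))]² = 44.9, so 45. After 5% loss: 45/0.95 = 47.4, so 48. The stated 50 is reproduced to within two patients. It is the size for two independent groups at 50% and 20%.

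**2. What the randomised arms would show under the Section 5 inputs.** Let q be the share of LTA patients above the PA cutoff. The protocol gives no value, so I assume 30–60%, independent of MA. Only baseline-high patients on prasugrel change.

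- TEG arm: 0.5 × 0.4 = 20%.
- LTA arm: 0.5 × (1 − 0.6q).
- Power = Φ{[d√n − 1.96√(2p̄(1−p̄))] / √(p₁(1−p₁) + p₂(1−p₂))}, with n = 47 evaluable per arm and no continuity correction.

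| q | LTA rate | Power | Evaluable per arm for 80% |
|---|---|---|---|
| 0 | 50% | 87% | 39 |
| 0.3 | 41% | 60.2% | 75 |
| 0.4 | 38% | 48.5% | 99 |
| 0.5 | 35% | 36.8% | 138 |
| 0.6 | 32% | 26.1% | 209 |

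The planned 50% versus 20% is the q = 0 row, in which no high-MA patient in the LTA arm receives prasugrel.

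**3. Before/after test if prasugrel adds nothing.** Take 48 per arm, MA bivariate normal across the two draws with correlation ρ, and the cutoff at the median (Section 2.0 places 69 at the 50th percentile). All tested patients start high, so every discordant pair goes one way and exact McNemar gives p = 2 × 0.5^b for b patients who fall below 69. Five falls give 0.0625 and six give 0.031, so six are enough.

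The chance that a baseline-high patient falls below the cutoff is arccos(ρ)/π. About 24 TEG-arm patients start high:

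| ρ | Chance of falling | Expected falls among 24 | Simulated rejection, TEG arm |
|---|---|---|---|
| 0.7 | 25.3% | 6.1 | about 58% |
| 0.8 | 20.5% | 4.9 | about 37% |
| 0.9 | 14.4% | 3.4 | about 12% |
| 0.95 | 10.1% | 2.4 | about 3% |

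Across all switched baseline-high patients in both arms there are more patients, so six falls are reached more easily. With about 46% above the PA cutoff and an MA–PA correlation of 0–0.3, rejection is about 91% at ρ = 0.7 and about 14% at ρ = 0.95.

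**4. Randomised comparisons under the same null.** TEG versus LTA in all patients (Fisher exact) rejects in 2–5%. TEG versus LTA among patients with baseline MA ≥ 69 rejects in 2–4%. Baseline MA comes from the first draw, before randomisation, so restricting to high starters keeps the protection of randomisation.

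**5. By drug received, all patients.** In the TEG arm every prasugrel patient starts high and every clopidogrel patient starts below 69. Pooled over arms, the baseline-high share is (25 + 25q)/(25 + 50q) = 81–73% on prasugrel and 25(1 − q)/(75 − 50q) = 29–22% on clopidogrel, for q = 0.3–0.6. The groups differ on the endpoint variable before any drug effect.

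**The case against.** **The design already points to the strategy comparison.** The Introduction calls the LTA-guided patients the control group, and Sections 2.0 and 5 speak of 50 per arm. An SAP that is not shown may name the test. This is fair: the absence of a named test is not the point. What stands is that the protocol's hypothesis is not what its randomisation tests, and that its two planning rates are not those of its two arms.

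**A reader might infer that the endpoint is framed by drug received.** The text does not support this. Every patient is reloaded with one drug or the other, so naming both fixes the time of measurement.

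**A reader might infer that the possible comparisons give opposite answers.** Under the Section 5 inputs they do not. Pooled by drug, 29–33% on prasugrel versus 22–29% on clopidogrel is a gap of 3–7 points (z = 0.35–0.78), far from significant. Before/after and by-strategy agree in direction. Among baseline-high patients, by drug, the result is 40% versus 100% in favour of prasugrel. That last reading fits the word persistence, and under the null it rejects in 4–5% of trials if PA is independent of MA, or 7–16% if they correlate at 0.3–0.5.

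**A reader might infer that a false positive is almost certain.** That would need several tests to be run and any success to be claimed; nothing in the protocol says so. The before/after rates also depend on an unstated retest correlation. At 0.95 the TEG-arm test does not exceed 5%, and before/after on the whole TEG arm's prevalence stays at 4–5%.

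**Conclusion.** The point holds in a limited form. The primary hypothesis, the randomised contrast and the Section 5 rates do not match. Tested as worded, the hypothesis rests on an uncontrolled change in patients selected for a high value, with false-positive rates of about 3–58% (TEG arm) or 14–91% (all switched baseline-high patients) for assumed retest correlations of 0.95–0.7. Comparison by drug received in all patients is confounded by the allocation rule. The randomised comparisons hold their error rate, but the all-patient one has about 60–26% power for q = 0.3–0.6. The retest correlation, the MA–PA correlation and q are assumptions, because the protocol gives none of them. The mismatch itself depends on none of these. The documents do not show that the endpoint is defined by drug, that the comparisons contradict each other, or that a false claim is nearly assured.

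**What to change.** In Sections B and 5:

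1. State that the deciding comparison is the proportion with MA ≥ 69 at 16–24 hours between the randomised TEG-guided and LTA-guided arms, analysed as randomised.
2. Assess the switching hypothesis by the same randomised comparison among patients with baseline MA ≥ 69, so that any fall is read against LTA-arm patients who also started high.
3. Label uncontrolled before/after and by-drug summaries descriptive, not used to accept the hypothesis.
4. Replace the 50% versus 20% planning rates with rates for the two arms that allow for prasugrel use in the LTA arm, and restate the power.

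**Cost.** No extra samples or assays are needed, because Section 3.0 runs both assays at both draws. It is still more than a change of wording. For 80% power the all-patient comparison needs 75 to 209 evaluable per arm for q = 0.3–0.6, so the sponsor must either enlarge the trial or accept and state lower power. The comparison among high starters sets 40% against 1 − 0.6q, that is 82%, 76%, 70% and 64%. With about 23.5 per arm (half of 47), the formula in step 2 of the working gives roughly 86%, 72%, 54% and 37%. These values are optimistic, since they assume that no patient's MA status changes except through prasugrel. The trial also gives up an uncontrolled before/after headline.

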1.0 Inclusion/Exclusion Criteria

Inclusion Criteria:

- Patients admitted with acute coronary syndrome (unstable angina, non-ST elevation myocardial infarction) and referred for coronary angiography.
- Current therapy with clopidogrel (at least 300mg loading dose, or 75mg po daily for >5 days)
- Age range 21-75 years.

Exclusion Criteria:

- Unable to give consent
- Age younger than 21 years, greater than 75 years
- History of stroke
- Body weight <60 kg
- Acute STEMI,
- Thrombocytopenia <100'000,
- requirement for chronic warfarin therapy

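### MA assigns treatment in the TEG arm and is the primary endpoint, yet the visible text sets no sampling rule for GpIIb/IIIa exposure, which the protocol says lowers MA; load-to-draw time is a lesser gap (minor, cheap to improve)

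*Protocol*

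**What the plan says.** **Entry.** Protocol section 1.0 requires "Current therapy with clopidogrel (at least 300mg loading dose, or 75mg po daily for >5 days". Section 2.0 restates the loading route: "All study candidates must have received at least 300mg of clopidogrel loading dose since admission". The maintenance route carries a minimum duration; the loading route carries no time condition. The exclusion list in section 1.0 has no GpIIb/IIIa item.

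**First draw.** Section 2.0 says: "Patients will have the first study blood draw performed prior to coronary angiography". The drug is then chosen "according to the results of the pre-cath TEG or LTA measurements": MA of 69 or more leads to prasugrel in the TEG arm, and ADP-induced aggregation above 42.9% does so in the LTA arm. The LTA rule is worded as "Patients in the LTA guided arm with high on treatment platelet reactivity to ADP", and section B (Specific Aims) speaks of "persistent high fibrin-platelet clot strength on clopidogrel".

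**Second draw.** The primary endpoint in section B is "Persistence of high tensile clot strength measured by TEG 16-24 hours after reloading of either clopidogrel or prasugrel". Section 3.0 runs both assays at both draws.

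**What the protocol knows about MA.** Section A (Introduction) reports that GpIIb/IIIa blockade with eptifibatide lowers MA significantly. It also suggests that insufficient P2Y12 inhibition may explain only part of the risk that goes with high clot strength.

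**Data.** The list in section 3.0 includes the patient's current medications. It is expressly open-ended, but it does not name load time, draw times or GpIIb/IIIa use.

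**A limit on this reading.** Section 2.0 adds: "The enrollment and study process is depicted in a Fig 1". That figure is not available here and might carry draw timing.

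**The concern.** The protocol names a drug class that moves its own key measurement, then leaves that class out of the sampling rules. This matters at two points.

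- *Baseline.* A GpIIb/IIIa inhibitor given before the first draw could bring a patient whose MA is otherwise high below 69. In the TEG arm that patient stays on clopidogrel. A wrong assignment cannot be undone in analysis.
- *Follow-up.* Exposure during the procedure could make a persistently high MA read as resolved at 16-24 hours, if the effect lasts that long.

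A second, weaker concern is the first draw's link to clopidogrel. The endpoint draw has a fixed window after reloading, but the assigning draw has no fixed relation to the first load. If some patients are sampled soon after loading, part of a later fall in MA could come from that first load.

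Both matter most for the primary hypothesis, which says that high MA on clopidogrel comes partly from inadequate P2Y12 inhibition and that switching to prasugrel corrects it. That invites a before-after reading in switched patients, where a late effect of the first load or a GpIIb/IIIa effect would be credited to prasugrel.

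**Working it through.** **Inputs.** From section 5: 50% of patients have MA of 69 or more at baseline, and switching resolves 60% of them, leaving 20%. From sections 2.0 and 5: 50 patients per arm. The documents give no frequency of GpIIb/IIIa use, no duration of its effect, no load-to-draw times and no onset time. Every count of affected patients below is therefore an assumption, used for scale only.

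**The plan's own figures.** In the TEG arm, 50 × 0.50 = 25 patients have high MA. Of these, 25 × 0.60 = 15 resolve and 10 persist; 10/50 = 20%, as the plan states. The conversion rate is 15/25 = 60%, with an exact (Clopper-Pearson) 95% interval of 39% to 79%. The sample size is not in dispute: 50% versus 20%, two-sided alpha 0.05, power 0.80 and a continuity correction give 45 per arm, and 45/0.95 rounds up to 48, close to the stated 50.

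**Weight of one patient.** 1/25 = 4 points of the switched group; 1/50 = 2 points of the arm.

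**GpIIb/IIIa exposure before the first draw.** Suppose j patients with truly high MA read below 69 and stay on clopidogrel.
- If none of them resolves, TEG-arm high MA at follow-up is [0.4 × (25 − j) + j]/50.
- j = 1: (9.6 + 1)/50 = 21.2%. j = 3: (8.8 + 3)/50 = 23.6%. j = 5: (8 + 5)/50 = 26.0%.
- If they resolve at 60% on clopidogrel too, the figure stays at 20%.
- The switched group shrinks from 25 to 24, 22 or 20.

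**Procedural GpIIb/IIIa exposure.** Suppose m of the 10 persisters read below 69 at 16-24 hours. Apparent conversion is (15 + m)/25.
- m = 1: 64%. m = 2: 68%. m = 3: 72%.
- If the effect has gone by 16-24 hours, m = 0 and nothing changes.

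**Early draw after a load.** Suppose k extra patients read high only because they were sampled early.
- If they resolve at 60%, (15 + 0.6k)/(25 + k) = 60% for any k.
- If all resolve, (15 + k)/(25 + k) gives 16/26 = 62% (k = 1), 18/28 = 64% (k = 3) and 20/30 = 67% (k = 5).

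The two GpIIb/IIIa routes pull the TEG-arm persistence rate in opposite directions, so no net direction can be claimed.

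**The case against.** *A loaded patient is on clopidogrel by the protocol's own definition.* Section 1.0 counts a load as current therapy. No passage demands full effect, and no onset time is given. A reader might infer that an early draw breaches the on-treatment condition. The documents do not support that, so the load-to-draw point is a possibility and not a breach. For MA it can in any case be only partial, given the Introduction's view of P2Y12 inhibition.

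*The comparison of arms is largely protected.* Patients are randomised after the first draw, so patients exposed or sampled early at baseline are expected equally in both arms. A reader might infer that the trial is biased toward prasugrel or toward the TEG strategy. That does not follow: what remains between arms is mainly misassignment and dilution. For procedural exposure this assumes that use does not depend on arm, and nothing in the text says that it does. The wrongful credit to prasugrel arises only in a before-after reading, which the hypothesis permits but no visible analysis specifies.

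*The trial cannot be shown to lose power.* Any power figure would need an assumed share of masked readings, and the documents supply none.

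*The data list is open-ended.* A reader might infer that exposure will go unrecorded. The text does not say so; it only fails to name these items.

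*The missing figure might fix draw timing.* That stands as a limit on any claim of absence.

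What survives is that the protocol itself states that this drug class lowers MA, and MA both assigns treatment and decides the endpoint. Neither draw has a rule for it in the visible text, and no analysis can repair a wrong assignment.

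**Conclusion.** The point holds as a minor, cheap improvement. Its firm part is GpIIb/IIIa exposure, and within that the baseline draw, where the consequence is a changed assignment. The follow-up part depends on an effect lasting to 16-24 hours, which is not documented. The load-to-draw part is secondary and conditional on an onset time that is not given.

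Size and direction are unknown. On section 5's assumptions, each affected patient is at most 4 points of a switched group of about 25. All the illustrated conversion rates (60% to 72%) lie inside the 39% to 79% interval that sampling error alone would give. A few affected patients would therefore matter modestly. The conclusion rests on the visible text and would narrow if Fig 1 already sets draw timing.

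**What to change.** These changes concern sampling and data only; clinical care stays unrestricted.

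1. In sections 2.0 and 3.0, state that the baseline study sample is taken before any GpIIb/IIIa inhibitor, or that the patient is not randomised on that sample.
2. In section 3.0, add by name to the data list: time of the clopidogrel load, time of each draw, and GpIIb/IIIa use with its timing. Then examine the 16-24 hour endpoint, and the conversion rate in switched patients, with exposed and early-draw patients set apart.
3. A minimum interval between load and baseline draw, chosen by the sponsor, is optional. It would tighten the on-treatment meaning of the first reading but narrow the population, so it is a trade-off and not a requirement.

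If Fig 1 already fixes draw timing, repeat it in sections 1.0 and 2.0.

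Cost: a short amendment, a few more recorded fields, and slightly fewer eligible ACS patients. The 16-24 hour window is unchanged.

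### Section 1.0 does not exclude active or recent clinically significant bleeding, and section 2.0 switches patients to prasugrel on an assay value with no stated bleeding check

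*Protocol*

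**What the plan says.** Section 1.0 gives seven exclusions: inability to consent, age outside 21 to 75, previous stroke, weight below 60 kg, acute STEMI, platelets below 100,000 and, last, "requirement for chronic warfarin therapy". To be included, a patient must already be taking clopidogrel (a load of at least 300 mg, or 75 mg daily for more than 5 days).

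Section 2.0 enrols patients before angiography, "after screening for appropriate candidates", and randomises those who go on to PCI. Treatment then follows the assay: "The subject will then be switched to prasugrel or continue on clopidogrel according to the results of the pre-cath TEG or LTA measurements". The cutoffs for prasugrel are MA ≥ 69 in the TEG arm and PA > 42.9% in the LTA arm. On dosing: "Patients assigned to prasugrel will receive 60mg po loading dose, and then remain on 10mg po daily". On the other side, "patients assigned to remain on clopidogrel will receive 300mg clopidogrel loading dose in the cath lab", followed by 75 mg daily. The section also refers to a flow chart ("The enrollment and study process is depicted in a Fig 1"), which is not visible in the copy reviewed.

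Section A says that prasugrel reduces ischaemic events more than clopidogrel does but that "it also carries an increased risk for significant bleeding". Section B lists bleeding as secondary endpoint b: "Occurrence of bleeding events according to TIMI minor/major criteria over 6 months follow-up".

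**The concern.** The protocol recognises that its stronger drug causes more significant bleeding, and then gives that drug by a rule that looks only at a laboratory value. Neither the eligibility list nor the assignment rule asks whether the patient is bleeding or has recently bled.

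What is at stake is the safety of a small group: patients whose clinicians accepted clopidogrel and PCI despite a recent bleed, but who would be poor candidates for a step up in platelet inhibition. Eligibility and treatment-assignment safety rules belong in the protocol, so a statistical analysis plan that is not shown would not be expected to supply them.

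**Working it through.** The plan gives no figure on bleeding, so the check is mainly a reading of the rules.

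**Step 1. What the exclusions cover (section 1.0).**

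| Exclusion | Bears on bleeding risk? | Names active or recent bleeding? |
|---|---|---|
| Unable to consent | no | no |
| Age outside 21–75 | yes (upper limit) | no |
| Previous stroke | yes | no |
| Weight < 60 kg | yes | no |
| Acute STEMI | no | no |
| Platelets < 100,000 | yes | no |
| Chronic warfarin | yes | no |

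Five of the seven bear on bleeding risk. None names bleeding itself.

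**Step 2. Follow one patient through the rules.** Take a 60-year-old weighing 80 kg with non-ST-elevation infarction, normal platelets, no stroke, no warfarin, a 300 mg clopidogrel load, and a recent clinically significant bleed. All seven exclusions are passed. If the patient proceeds to PCI, is randomised to the TEG arm and has MA ≥ 69, section 2.0 gives prasugrel 60 mg, then 10 mg daily. The same happens in the LTA arm with PA > 42.9%. No contraindication check or investigator override is stated.

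**Step 3. Look for a safeguard elsewhere.**
- Section 2.0 mentions screening of candidates but attaches no criterion to it.
- Section 3.0 lists baseline data, expressly not exhaustive. A blood count and medication list are included; bleeding history is not listed.
- Section 4.1 has a two-physician board that monitors progress at least annually, and section 4.2 has the investigator and coordinator review immediate adverse events. Section 2.0 adds a telephone call at 6 months. None of these is a check before the loading dose.
- Section 4.5 covers withdrawal at the participant's request only.

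**Step 4. Can the gap be counted?** The number affected would be

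switched patients × share with a recent bleed × share of those fit for clopidogrel but not for prasugrel.

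Only part of the first factor is in the protocol. Section 5 assumes 50% with MA ≥ 69, so about 50 × 0.50 = 25 TEG-arm patients are switched. The share above the LTA cutoff is not given, and neither are the second and third factors. The product cannot be formed from the documents.

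**Step 5. Does the fix disturb the sample size?** The inputs in section 5 are 50% against 20%, power 0.8, alpha 0.05 (sidedness not stated; two-sided taken here) and 5% loss. Then

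n = [1.96·√(2 × 0.35 × 0.65) + 0.842·√(0.5 × 0.5 + 0.2 × 0.8)]² / 0.30² ≈ 38.5, so 39 per arm.

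With continuity correction this becomes 45, and 45 / 0.95 = 47.4, so 48 per arm. That is within 2 of the stated 50. No bleeding criterion enters the calculation.

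**The case against.** The strongest reply is that clinical practice already does this work. Every patient has been judged fit for clopidogrel and then for PCI, the study is open label, standard hospital care applies, and five exclusions remove recognised bleeding-risk groups. Patients who stay on clopidogrel are reloaded as well, so the added hazard is only the difference between the two drugs. The screening step may also be spelled out in Fig 1.

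Most of this stands, and it is why the gap is small. It does not close it. Fitness for clopidogrel is not fitness for a drug the protocol calls riskier, and the five exclusions are indirect markers that the patient in step 2 passes. As Fig 1 is not visible, the claim is limited to the visible text.

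Stronger readings are tempting but unsupported:
- A reader might infer that the plan ignores bleeding risk. The exclusions show otherwise.
- A reader might infer that some number of the 100 patients would be harmed or wrongly treated. The documents give no bleeding frequency, and any assumed rate of recent bleeding would also include patients for whom prasugrel is still acceptable.
- A reader might argue that having bleeding as a secondary endpoint makes the eligibility list wrong. Measuring an outcome does not do that.

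**Conclusion.** The point holds as a limited safety gap. In the visible text no eligibility criterion and no step before the loading dose addresses active or recent bleeding, while the switch to the higher-risk drug depends only on the assay. Following the rules exactly would give a recent bleeder prasugrel.

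The group is probably few patients. That is a judgement resting on prior selection for clopidogrel and PCI and on the existing exclusions, not a calculated figure. It also assumes that Fig 1 contains no bleeding check. The primary endpoint, its comparison between arms and the sample size are not called into question. The change should be made because it is cheap and protects patients, not because the trial fails without it.

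**What to change.** Add to section 1.0 the exclusion: *active bleeding, or recent bleeding that in the investigator's judgement makes prasugrel unsuitable*. The study clinicians should choose the look-back period and write it into the protocol before enrolment starts. A plain clinical criterion is preferable to grading past bleeds on the TIMI scale, because section 3.0 does not list the history that grading would need.

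Re-confirm the criterion at randomisation, before the loading dose. Enrolment precedes angiography and loading follows the decision to perform PCI, so bleeding status can change in between. Making the check before the arm is disclosed, and for every candidate whatever the assay result, avoids exclusions after allocation.

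The cost is one line in section 1.0, one bleeding-history question added to the baseline data, one brief check before allocation, and a few candidates lost.
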